DSMB: The DSMB consists of an independent neurologist, an endocrinologist, and a statistician. It will convene any time an adverse event \geq grade 3 occurs and routinely at 25%, 50%, 75%, and 100% enrollment. All serious adverse events will be promptly and simultaneously reported to the IRB, the DSMB and the Independent Research Monitor. Only serious adverse events (SAEs) that would also meet the definition of an Unanticipated Problem Involving Risks to Subjects or Others (UPIRTSOs) that are related to the protocol will be promptly reported to the United States Army Medical Research and Materiel Command Office of Research Protections Human Research Protection Office HRPO (USAMRC ORP HRPO).

Independent Research Monitor: The PI, [name], has appointed [name], a trained neurologist, as the Independent Research Monitor. [name] will provide independent safety review and will have the

authority to stop the research study; remove an individual subject from the research study; and will take any steps to protect the safety and well-being of the subjects until the IRB can assess the problem or event. The independent research monitor must review all unanticipated problems involving risks to subjects or others (UPIRTSO), but not all SAEs. The monitor will review the SAEs if they also meet the definition of a UPIRTSO and will provide an unbiased written report of the event. The Research Monitor will comment on the outcomes of the event or problem and the relationship to participation in the study. Additionally, the research monitor will indicate whether she concurs with the details of the report provided by the principal investigator.

Analytic Plan

Aim 1. Safety data will be analyzed as they are captured in real time. Assessments will focus on AEs (including study treatment tolerability assessments, laboratory evaluations, vital signs, and physical examination). The incidence rate of AEs will be recorded by system organ class, severity, and by relationship to the study treatment. Tolerability analysis will be based on the number (%) of subjects who failed to complete the study due to adverse events. Lab values for each parameter will be summarized by shift tables. For quantitative parameters, summary statistics for actual values and change from baseline will be presented. Changes in the first 24 weeks will be compared between groups using mixed effects regression analyses to account for the longitudinal nature of the data using random subject-specific intercepts and slopes.

Aim 2. Summary statistics (mean ± standard deviation, median and interquartile range, or number and percentages) will be used to characterize the outcomes. For each cognitive outcome, to evaluate variability in the estimated means across groups, assuming that the within-group means are normally distributed, a one-way ANOVA will be conducted at the follow-up visits during the first 24 weeks. If the within-group data are strongly non-Gaussian, a Kruskal-Wallis test will be used. A mixed effects longitudinal model will also be used to test whether any differences across groups exist at the follow-up visits within the first 24 weeks. Further, models accounting for covariates of interest, including the HOMA-IR, body composition, body mass index, age, sex and depression, will be used. For within-person changes in measures at follow-up compared to baseline, paired t-tests will be used. We will also evaluate the SDMT at each study visit and other MACFIMS outcomes at week48 to establish the longevity of any therapeutic response to insulin.

Aim 3. For the biomarker outcomes, to evaluate variability in the estimated means across groups, assuming that the within-group means are normally distributed, a one-way ANOVA will be conducted at the follow-up visits during the active treatment phase. If the within-group data are strongly non-Gaussian, a Kruskal-Wallis test will be used. A mixed effects longitudinal model will also be used to test if differences across groups exist at follow-up visits. For within-person changes in measures at follow-up compared to baseline or before versus after calorie restriction days, paired t-tests will be used. Correlations between the biomarkers will be assessed. A bootstrap of subjects will be used to obtain 95% equal confidence intervals for these measures. We will also evaluate the biomarker changes after study therapy ends.

Sample Size and Power: Sample size estimates are difficult given the novelty of the project but are based on the goal of detecting a benefit of insulin on cognition. In a pivotal study of two doses of intranasal insulin versus placebo in participants with mild cognitive impairment or mild to moderate Alzheimer's Disease, the Dementia Severity Rating Scale score improved over the four-month treatment course in those receiving intranasal insulin.³⁴ Using the scores in the 10 IU twice a day group, given a two-sided alpha of 0.05 and beta 0.20 (80% power), assuming 3 follow-up cognitive tests and a correlation between baseline and follow-up results of 0.5, 29 subjects per group are required. To account for drop-outs and for the three-arm design, a total of 35 subjects per group is planned. With SDMT as the outcome, for a two-arm design, this sample size confers 80% power (assuming SDMT standard deviation of 9 points and two-sided alpha of 0.05) to detect a 6-point improvement in SDMT which seems reasonable considering that transcranial stimulation with cognitive training

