PROTOCOL TITLE: INTRANASAL INSULIN FOR IMPROVING COGNITIVE FUNCTION IN MULTIPLE SCLEROSIS

DATE: November 20, 2020

VERSION: 2.4

SYNOPSIS

This will be a randomized, double-blind, placebo-controlled phase I/II pilot study. Participants will be randomized to intranasal insulin 10 international units (IU) twice a day, 20 IU twice a day, or placebo for 24 weeks. Insulin will be administered intranasally using the novel ViaNaseTM controlled particle dispersion system, allowing for direct delivery of the medication to the nasal epithelium, leading to maximal transport to the CNS (Kurve Technology, Lynnwood, WA).³⁴ Cognitive assessments will occur at baseline and throughout the 24-week trial, as well as for a period of 24 weeks after discontinuation of the intervention, to evaluate the impact of insulin on cognitive performance as well as the longevity of the treatment response. Biomarkers of cellular stress, neuronal injury, oxidative stress, inflammation, and energy metabolism will be assessed at baseline and at subsequent visits. Stored specimens will be acquired for more detailed future mechanistic studies if intranasal insulin does appear to be safe and effective.

INTRODUCTION

Cognitive impairment is common in and devastating to people with MS. MS is a common, chronic, central nervous system (CNS) disease characterized by inflammation, demyelination, and neurodegeneration. One of the most devastating symptoms of this disease is impaired cognitive function, which is common and present in over 60% of individuals with MS.¹⁻³ MS-related cognitive impairment is associated with lowered quality of life ⁴ and reduced functional capacity, including loss of employment,⁴⁻⁷ impaired social relationships,⁸ compromised driving safety,⁷ and poor adherence to treatment.⁹ Impaired cognitive functioning has been observed early in the disease, sometimes even before diagnosis,¹⁰ and cognitive function has been shown to decline longitudinally, both over the short- and long-term.¹¹⁻¹³ Several cognitive domains are impacted in people with MS, including attention, memory, executive functioning, and especially processing speed.^{2, 10, 14-18}

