Insulin administration has been shown to improve memory and learning in healthy people and in those with neurodegenerative diseases (see Table 1). Intranasal insulin has shown to have neuroprotective and restorative effects in several human clinical trials. In a recent randomized, double-blind, placebo-controlled study with over 100 people suffering from amnestic mild cognitive impairment or Alzheimer's Disease, intranasal insulin preserved cognitive function in both selective cognitive domains and more globally compared to placebo.³⁴ The insulin-treated patients also did not show a decline in measures of brain metabolism, whereas the placebo-treated participants did show decreases in fluorodeoxyglucose ¹⁸F uptake in various lobes (parietotemporal, frontal, precuneus, and cuneus). Further, improvements in episodic memory persisted for several weeks after treatment cessation. Overall, these findings suggest that intranasal insulin not only affects cognitive function acutely, but that over time, there may be associated structural changes that lead to a more permanent treatment benefit. Since cognitive dysfunction is very common in MS and can be devastating, a treatment intervention (i.e., intranasal insulin) that can help both acutely and longitudinally is worth pursuing.

| REF. | INTRANASAL INSULIN DOSE | SUBJECTS | ASSESSMENT |
|---------------|-------------------------------|-----------------|---|
| Benedict 2004 | 160 IU (long-term) | Healthy | Word list (immediate, delayed recall |
| Reger 2006 | 20 or 40 IU (acute) | Probable AD or | Story recall (immediate, delayed recall) |
| | | MCI vs. healthy | Word list (immediate, delayed recall) |
| Benedict 2007 | 20 IU Aspart vs. 20 IU | Healthy men | Word list (immediate recall) |
| | Regular (long term) | | Word list (delayed recall) |
| Benedict 2008 | 160 IU (acute) | Healthy, normal | Digit span, object location (immediate recall) |
| | | weight, no meds | Mirror tracing (immediate recall) |
| Hallschmid | 160 IU (long-term) | Obese men | Word list (delayed recall) |
| 2008 | | | Word list (immediate recall) |
| Reger 2008 | 20 IU (long term) | AD or MCI | Memory score (immediate/ delayed recall ratio) |
| | | | Voice onset time (immediate/delayed recall ratio) |
| Reger 2008 | 10, 20, 40, 6 0 IU | AD or MCI | Story recall (immediate recall or delayed recall) |
| | (acute) | vs. healthy | Word list learning (immediate & delayed recall) |

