for eligibility, even if they haven't had a recent clinic visit. For MS Center patients that have not taken an SDMT or PST test, we will use an oral consent process to administer the SDMT test and determine eligibility. SDMT or PST test results obtained within 3 months of the baseline visit will be considered as proof of eligibility for the study and may be screened in person or by phone. The study coordinator will only approach MS Center patients of physicians on the study team or those referred by their treating physician. In addition to the above recruitment strategies, we will obtain home-based PST screening test for our MS patients that have iPADs (Air, Air 2, and iPAD 2017), as the PST app is now available. This will allow for remotely screening potential subjects that have transportation and/or mobility limitations. If at any time point, enrollment is less than 85% of the target, we will interview subjects who have declined to participate to determine the deterrents to enrollment; we will then implement alterations in recruitment needed to enhance enrollment.

Study Treatment: Intranasal insulin (Novolin R, Novo Nordisk, Princeton, NJ) will be evaluated in two doses (10 IU twice a day, 20 IU twice a day) and compared to the sterile diluent (Eli Lilly and Company – NDC:00002-0800) (1:1:1 randomization, stratified by relapsing versus progressive MS). The 20 IU dose will consist of insulin. The 10 IU dose will be a diluted mixture comprised of normal saline and insulin. The study drug, insulin, has a distinct smell. In order to preserve study blinding, we will use the Lilly sterile diluent, which has a similar odor as the insulin, to preserve blinding. The study drug and placebo (Lilly diluent) will be prepared by the Johns Hopkins Investigational Drug Service and will appear identical to maintain blinding. A nasal drug delivery device (Kurve Technology, Lynnwood, WA) will be utilized to ensure optimal exposure of the olfactory epithelium. The treatment regimen was chosen to match that of a recent successful pilot study in Alzheimer's Disease.³⁴ Evaluating two doses will allow for the possibility that any benefit of insulin may be non-linear.

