| Medication review | Х | Х | Х | Х | Х | Х |
| Vital signs | Х | | Х | Х | | |
| Neurologic (EDSS) exam | Х | | | | | |
| MS Functional Composite | X | | X*** | X*** | | |

| Adverse event assessment | | Х | Х | Х | X | Х |
|---------------------------------|-----|---|-----|-----|---|---|
| Biomarker evaluation | Х | | Х | Х | | |
| Stored blood for future studies | X\$ | | X\$ | X\$ | | |
| DXA scan | Х | | | | | |
| Pregnancy assessment* | X* | Х | Х | Х | | |
| MACFIMS battery | Х | | Х | Х | | Х |
| Sleep questionnaires | Х | | Х | Х | | Х |
| Depression and quality of life | X | Х | Х | Х | Х | X |
| Suicidality evaluation | X | Х | Х | Х | Х | X |

*Pregnancy test at baseline; document last menstrual period/adequate pregnancy prevention plan at virtual follow-ups (for women of childbearing potential)

will convert to virtual follow-up with activities equal to week 6 if stay-at-home orders recur Items that are in **bold will be done either virtually or in-person until operations are fully normalized with respect to COVID-19 pandemic; in addition, some aspects of the MACFIMS neuropsychological battery can (and will) be done virtually as well

***timed 25-foot walk only

[&]Consent will be reviewed at length virtually within the week prior to the day of the visit, with all questions asked at that time. At the baseline visit, patients will be given the opportunity to ask any remaining questions and can sign during the teleconsent, if capable, or will sign at the time of the baseline visit.

% if COVID-19 pandemic is lifted, we will still complete this visit in-person; we will accept a study window that extends 3 months beyond week 48 if there is indication at that time, even if the pandemic is still affecting safety, that it will soon be safe again (e.g. vaccine developed or clear evidence of critical percentage of population has already been infected, fully operational at JHU)

If a severe COVID-19 outbreak occurs again such as occurred in the spring of 2020, we will conduct all followup assessments by video or phone until such time as it is safe to pursue the modified schedule, as above, or resume the originally-planned schedule.

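### Under the COVID-19 schedule no SDMT is marked at week 36, although Protocol Aim 2 and the SAP use that visit to judge how long a benefit lasts

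*Protocol*

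**What the plan says.** **Purpose.** The Protocol Synopsis gives treatment as "20 IU twice a day, or placebo for 24 weeks". It plans cognitive testing during treatment "as well as for a period of 24 weeks after discontinuation of the intervention", to assess the effect on cognition "as well as the longevity of the treatment response". The section on additional outcomes adds that the MACFIMS is followed after stopping to look for a decline.

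**Analysis.** Analytic Plan, Aim 2: "We will also evaluate the SDMT at each study visit and other MACFIMS outcomes at week48 to establish the longevity of any therapeutic response to" the study drug. SAP V.c describes the SDMT at baseline and weeks 6, 12, 24, 36 and 48. SAP VIII.c adds weeks 36 and 48 in a secondary analysis of a sustained effect after treatment ends.

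**Schedules.** The SDMT is part of the MACFIMS (Outcomes, Cognitive Assessments), and neither visit table has a separate SDMT row. The standard table marks the MACFIMS at weeks 0, 12, 24, 36 and 48. The COVID-19 table marks it at weeks 0, 12, 24 and 48. Week 36 remains as a virtual visit with adverse events, depression, quality of life and suicidality.

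**Footnotes to the COVID-19 table.** For week 48, "we will accept a study window that extends 3 months beyond week 48" if there are signs that it will soon be safe again. On remote testing, "some aspects of the MACFIMS neuropsychological battery can (and will) be done virtually as well"; the parts are not named.

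**The concern.** Two parts of the plan rely on a week-36 SDMT that the schedule in force during the pandemic does not mark. Staff who work from the table would not collect it, and the SAP's week-36 data would then come only from participants seen at that visit under the standard schedule. For the others, the off-treatment course would rest on a single point, at a time that may differ between participants by up to three months.

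At stake is the timing of any loss of benefit. A null result at week 48 would not separate a benefit that ended soon after week 24 from one that lasted two or three months. For a pilot meant to supply estimates for a later trial, that information is worth having.

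**Working it through.** **1. Reproduce the plan's figure.** Treatment ends at week 24 and the last visit is week 48. 48 − 24 = 24 weeks off treatment, which matches the Synopsis.

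**2. First off-treatment SDMT, nominal dates.**
- Standard table: 36 − 24 = 12 weeks.
- COVID-19 table, week 48 on time: 48 − 24 = 24 weeks.
- COVID-19 table, full extension: 3 months = 3 × 365.25 / 12 / 7 = 13.0 weeks, so 24 + 13.0 = 37.0 weeks off treatment (study week 61).

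**3. Visit windows.** With the usual ±5 days at both visits, the standard first test falls at 12 ± 10/7, or 10.6 to 13.4 weeks. The COVID-19 test falls between 24 − 10/7 = 22.6 weeks and 24 + 13.04 + 5/7 = 37.8 weeks (week 24 early, extension counted from the week-48 target). With the ±10 days allowed during the pandemic, the range is 21.1 to 38.5 weeks.

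**4. The passages side by side.**

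| Source | SDMT at week 36? |
|---|---|
| Standard visit table | Yes, within the MACFIMS |
| COVID-19 visit table | MACFIMS blank; no SDMT row |
| Protocol Aim 2 | Yes, at every study visit |
| SAP V.c and VIII.c | Yes, week 36 listed |

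**5. Rules for a late week 48.** SAP VIII.c requires the week-24 visit within 25 weeks. The SAP text available gives no matching rule for week 48. SAP VIII.f makes time linear but does not say whether it is nominal or actual. If nominal, a visit at week 61 would be analysed as week 48.

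**6. Illustration of size.** The half-lives below are assumptions; the documents give none. Start from the protocol's 6-point SDMT difference and let it decay after week 24: remaining difference = 6 × 0.5^(w/h), with w weeks off drug and half-life h.

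| Half-life | Week 36 (w = 12) | Week 48 (w = 24) | Week 48 + 3 months (w = 37) |
|---|---|---|---|
| 8 weeks | 2.1 | 0.8 | 0.2 |
| 12 weeks | 3.0 | 1.5 | 0.7 |
| 24 weeks | 4.2 | 3.0 | 2.1 |

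For scale, with SD 9 and 70 versus 35 participants (whole trial, no drop-out), the single-visit SE is 9 × √(1/70 + 1/35) = 1.86 points. For half-lives of 8 and 12 weeks, week 48 lies 0.8/1.86 = 0.4 and 1.5/1.86 = 0.8 SE from zero. Week 36 lies 2.1/1.86 = 1.1 and 3.0/1.86 = 1.6 SE from zero. A week-36 test therefore carries more information, but alone it would usually not be significant either. Its value lies in estimating the course of decline.

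**The case against.** A reader might infer that the COVID-19 table removes the only informative off-treatment SDMT, so that longevity cannot be assessed. The documents do not support that, for several reasons.

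- **A blank MACFIMS cell does not prove that no SDMT is given.** Aim 2 separates the SDMT (every visit) from the other MACFIMS outcomes (week 48). The SAP lists an SDMT at week 6, where even the standard table marks no MACFIMS. This stands: the firm finding is an unreconciled conflict. For the other MACFIMS outcomes, Aim 2 needs only week 48, which the COVID-19 table keeps.
- **The schedule is temporary and the extension conditional.** This stands: only visits held under the modified schedule are affected, and 37 weeks is a maximum.
- **A late test is still useful.** This stands: it shows whether a benefit persists at about six months or later.
- **No time of fade is stated.** The Introduction reports that "improvements in episodic memory persisted for several weeks after treatment cessation", but for episodic memory in mild cognitive impairment or Alzheimer's disease, not for the SDMT in MS. It also raises the possibility of a more lasting benefit. Week 48 therefore cannot be said to fall after an expected fade.
- **Remote feasibility is only partly documented.** The Recruitment wording "may be screened in person or by phone" concerns eligibility and does not clearly describe remote SDMT administration. Against this, week 48 in the same table is headed virtual and keeps the MACFIMS, and the protocol already recommends the oral form of the SDMT for MS.
- **The SAP does part of the work.** It describes missing SDMT data by arm and time, and it stratifies at 13 March 2020. Neither step replaces a measurement that was not taken.

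**Conclusion.** The point holds as a conflict between the COVID-19 schedule and the analyses it is meant to feed. If the table is followed, affected participants have their first off-treatment SDMT 24 weeks after week 24, or about 37 weeks at most, instead of about 12. That test can establish persistence to its own date. It cannot date an earlier loss, and it would miss a benefit that lasted only to around week 36.

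This assumes that dosing ends at week 24, that dates are nominal, and that no SDMT is given outside the MACFIMS row. The documents do not state how many participants are affected. The half-life figures only illustrate the point and do not support a claim about power. The primary SDMT analysis runs through week 24 and is unaffected; the weakness is confined to the secondary question of sustained effect, in a pilot that does not expect conclusive evidence of efficacy. It is still worth correcting, because the visit already takes place.

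**What to change.** 1. In the COVID-19 table, mark the oral SDMT at the virtual week-36 visit, given remotely, and record the mode of testing (remote or in person) at every visit. This brings the table into line with Aim 2 and SAP VIII.c. A separate SDMT row in both tables would also settle week 6.
2. In the SAP, state that off-treatment time is modelled as actual weeks since the last dose, so that a week-48 visit held up to 3 months late is not analysed as week 48.

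A separate week-48 estimate restricted to visits near the target date is optional, and largely redundant once actual time is used.

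Cost: one brief remote test at a visit that already exists, plus edits to the schedule and SAP. The main downside is a possible difference between remote and in-person scores. It is balanced across arms in expectation, and recording the mode lets it be examined.

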All study visits will be scheduled for the morning to reduce variability in cognitive function related to the time of day. At baseline, fasting laboratory testing will be performed, including a hemoglobin A1c test and insulin level. All subjects will then be given breakfast prior to completing cognitive testing. For follow-up visits, all subjects will complete the MACFIMS battery after eating a usual meal (if the participant came without having eaten, breakfast will be provided to them) and prior to taking the morning dose of study treatment. Unscheduled visits will occur if any safety issue arises.

In order to ensure subjects (or their responsible caregivers) are able to use the medication as instructed, all subjects and caregivers (when relevant) will be instructed on the use of the inhaler and will be observed by a health care provider when performing their first dose administration at the time of the first visit.

Risks

Intranasal insulin

Intranasal insulin has been shown to be safe and tolerable in other populations and patient groups, but it has never been studied in people with MS. The most common side effects related to irritation of the nasal passages. Giving insulin through the nose did not result in lower circulating glucose levels in other studies, but the first 15

people in this study will be monitored for this potential risk by testing a fingerstick blood glucose level periodically for 90 minutes after the first dose of intranasal insulin (see Safety section under **Outcomes** on page 10).

Insulin, given by the more traditional subcutaneous route, has the following potential risks:

Hypoglycemia: Common symptoms of hypoglycemia include sweating, dizziness or lightheadedness, shakiness, hunger, a fast heartbeat, tingling of the hands, feet, lips or tongue, trouble concentrating, confusion, blurry vision, slurred speech, anxiety, irritability, or mood changes, or headache. Very low blood sugar can cause loss of consciousness, seizures, or temporary or permanent brain problems or death. Mild hypoglycemia can be treated by drinking or eating something sugary right away (fruit juice, sugar candies, or glucose tablets).

Hypokalemia: Hypokalemia can lead to breathing problems, low heartbeat, or death.

Allergic reaction: Common symptoms of an allergic reaction include a rash all over the body, trouble breathing, a fast heartbeat, sweating, and feeling faint.

Weight gain or swelling of the arms and legs.

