Exploratory Biomarkers Plasma and/or PBMCs will be collected at baseline, week 12, and week 24 visits (except if COVID-19 related shutdown does not permit follow-up blood collection or lab-based processing) and will be isolated and cryopreserved for batch analyses in the labs of [name] or [name]. Inflammatory (cytokines, lymphocyte subsets), metabolic (Kreb's cycle substrate, fatty acids), cellular stress (ceramides, sphingomyelin) and neurotrophic (BDNF) measures, as well as markers of oxidative stress (protein carbonyls, 8-isoprostane, nitrotyrosine, and 4-hydroxynonenal adducts [lysine and histidine]), will be quantified. Since our data show oxidative stress biomarkers and elevated ceramides in plasma of MS patients and recent work shows

the brain has lymphatics, explaining how brain metabolites return to the periphery, blood biomarkers are a relevant and convenient way to monitor CNS metabolism.⁶²

Additional Outcomes and Assessment of Covariates In order to identify and, if needed, adjust for comorbid depression, the Beck Depression Inventory will be administered at each study visit. Health-related quality of life will also be assessed utilizing the FAMS. We will also evaluate how overall sleep quality in people with MS impacts health-related quality of life. We will also evaluate for occult insulin resistance or differences in metabolism in several ways. We will evaluate dual-energy x-ray absorptiometry (DXA) at baseline, which will help determine body composition, in particular bone density. We will also calculate an insulin resistance index, the homeostatic model assessment (HOMA-IR),⁶³ using baseline fasting glucose and insulin. Statistical models exploring these body composition and insulin resistance parameters as potential confounders or mediators will be evaluated. Finally, the MACFIMS, safety, depression, and health-related quality of life outcomes will be monitored after discontinuation of the insulin (or placebo) to evaluate for any decline in cognitive function associated with medication discontinuation.

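### No meal condition is set for follow-up biomarker blood, so paired tests against a probably fasting baseline cannot separate feeding from treatment

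*Protocol*

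**What the plan says.** Protocol, Study Visits (text after the schedule tables), on baseline: "At baseline, fasting laboratory testing will be performed, including a hemoglobin A1c test and insulin level". It continues: "All subjects will then be given breakfast prior to completing cognitive testing". So the order at baseline is fasting blood, breakfast, cognitive tests.

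The same paragraph on follow-up: "For follow-up visits, all subjects will complete the MACFIMS battery after eating a usual meal", with the proviso "if the participant came without having eaten, breakfast will be provided to them". This rule, and the placing of the battery before the morning dose, govern the MACFIMS only. Nothing states whether follow-up blood is fasting, where it falls relative to the meal or dose, or that time since eating is recorded. At week 6 the main schedule has a biomarker draw but no MACFIMS, so not even the indirect meal rule applies.

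Protocol, Exploratory Biomarkers: "Plasma and/or PBMCs will be collected at baseline, week 12, and week 24 visits". The main schedule table marks biomarkers at all six visits; the COVID-19 schedule marks weeks 0, 12 and 24. The measures include "metabolic (Kreb's cycle substrate, fatty acids), cellular stress (ceramides, sphingomyelin".

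Protocol, Analytic Plan, Aim 3 plans a one-way ANOVA (or Kruskal-Wallis) and a mixed model across arms. It then adds: "For within-person changes in measures at follow-up compared to baseline or before versus after calorie restriction days, paired t-tests will be used". No calorie-restriction days appear elsewhere in the protocol, so that phrase supplies no meal rule.

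The SAP sections available (III to IX) list no biomarker outcome and no adjustment for meal state. Fasting insulin, fasting glucose and HOMA-IR appear there only as baseline characteristics.

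**The concern.** The protocol controls meal state for cognitive testing and for baseline HOMA-IR, but not for the follow-up blood that Aim 3 depends on. Several Aim 3 markers belong to energy metabolism. I take it as a premise, since the documents are silent, that fatty acids and Krebs-cycle substrates respond to a recent meal. Because the study drug is itself a metabolic hormone, a change caused by breakfast would look like the change the trial hopes to see.

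A paired test against baseline within an arm has no internal control for this. A fasting-to-fed shift would appear in every arm, placebo included, and someone reading only the insulin arms could take it for a treatment effect. The Aim 1 change-from-baseline laboratory summaries share the weakness for any meal-sensitive analyte.

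**Working it through.** **Inputs from the protocol (Sample Size and Power).** 35 per arm; two-sided alpha 0.05; 80% power for a 10 ng/mL ceramide difference, with no SD given; baseline to follow-up correlation 0.5, stated for cognitive tests and borrowed here. With correlation 0.5, the SD of change is √(2 × (1 − 0.5)) = 1 marker SD, so one scale serves both steps below.

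**Assumptions.** Feeding shift d = 0.25, 0.5 or 1.0 SD; share fed at follow-up p = 100%, 70% or 50%, equal across arms; all fasting at baseline; no drug effect except in the power figures.

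**Step 1: the plan's own biomarker figure.** Without an SD, the 80% cannot be checked forward. Solving back:

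SD = 10 / ((1.960 + 0.842) × √(2/35)) = 14.9 ng/mL.

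This is the SD that the statement implies, and step 3 uses it.

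**Step 2: within-arm paired t-test.** The mean change is p·d, its SD is √(1 + p(1 − p)d²), and the noncentrality is p·d·√35 divided by that SD. The critical t on 34 df is 2.032. Example with p = 0.7 and d = 0.5: mean 0.35, SD √1.0525 = 1.026, noncentrality 0.35 × 5.916 / 1.026 = 2.02, rejection rate 50%.

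| Share fed | d = 0.25 | d = 0.5 | d = 1.0 |
|---|---|---|---|
| 100% | 30% | 82% | >99% |
| 70% | 17% | 50% | about 95% |
| 50% | 11% | 29% | 73% |

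A simulation of 10,000 null trials agrees: 30%, 81% and 100% with all fed; 17%, 50% and 95% with 70% fed. With no feeding shift, which is what a matched draw achieves, the test rejects in 4.7% to 4.8% of trials.

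**Step 3: between-arm comparisons.** Each arm carries the same mean shift p·d, so the expected difference is zero. In the simulation the between-arm bias was at most 0.005 SD. Type I error was 4.7% to 5.3% for the ANOVA and 4.6% to 5.4% for two-arm change scores.

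The remaining cost is variance. The follow-up SD becomes 14.93 × √(1 + p(1 − p)d²), and the power for 10 ng/mL follows:

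| Shift | SD at 50% / 70% fed | Power at 50% / 70% fed |
|---|---|---|
| 0.25 | 15.05 / 15.03 | 79% / 79% |
| 0.5 | 15.39 / 15.32 | 78% / 78% |
| 1.0 | 16.69 / 16.43 | 71% / 72% |

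If everyone is fed, the SD and the power do not change. The ceramide scale is used only because it is the one biomarker with a power statement; the documents do not say whether ceramides are meal-sensitive.

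**The case against.** The strongest reply is that the trial is randomized 1:1:1 and double-blind with concurrent placebo, that all arms follow the same visit rules, and that Aim 3 lists the between-group tests before the paired ones. A shift present in every arm, placebo included, is how a reader would recognise that it is not an insulin effect. Aim 3 is exploratory, and many of its markers (cytokines, lymphocyte subsets, BDNF, oxidative markers) are not argued to depend on meals. All of this stands, and it limits the point to within-person change in meal-sensitive markers.

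Three stronger readings are tempting, and the documents do not support them:

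- A reader might infer that the estimated effect of insulin on biomarkers is confounded by feeding. Step 3 shows that it is not, unless feeding differs by arm, and nothing in the plan suggests that.
- A reader might infer that the protocol prescribes fasting research blood at baseline and fed blood at follow-up. Neither is stated. The baseline sentence names HbA1c and insulin, and a follow-up draw could precede the breakfast provided. That would restore a fasting state only for those who arrive unfed. The condition is unspecified; it is not a declared mismatch.
- A reader might infer that draws after the morning dose mix acute with sustained drug effects, because the Introduction says CSF insulin rises within 30-40 minutes. That statement concerns CSF, and the same sentence reports no adverse effect on blood glucose or insulin. It supports recording dose time and no more.

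**Conclusion.** The point holds for the paired t-tests of Aim 3. As written, a significant change from baseline in a meal-sensitive marker could be produced by breakfast alone. Across the assumed ranges, the false-positive rate per arm runs from 11% (0.25 SD, half fed) to over 99% (1.0 SD, all fed), against a nominal 5%.

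This rests on the baseline research sample being the fasting draw, on the markers responding to meals, and on assumed values for shift size and share fed. Between arms the cost is precision only, and it is small unless the shift is large. The SDMT analysis and baseline HOMA-IR are unaffected. This is a cheap improvement to an exploratory aim and does not threaten the trial's main conclusions.

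**What to change.** - **Protocol, Study Visits.** State that biomarker blood at in-person follow-up visits is drawn in the same state as at baseline: fasting, before the breakfast already provided and before the MACFIMS. State also that the baseline research sample is part of the fasting draw, if it is. Record the time of last meal and last dose with every sample.
- **Protocol, Analytic Plan, Aim 3.** Make the baseline-adjusted between-arm contrast the biomarker test of treatment, and label within-arm paired tests descriptive.
- **Samples already drawn.** Adjust for fasting status where it is known. Where it was not recorded, do not read paired changes in meal-sensitive markers as treatment effects.

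The cost is a short amendment and a line in the visit reminder. Visits are already in the morning and breakfast is already offered to those who need it. The downside is that participants travel fasting to the follow-up blood-draw visits: two under Exploratory Biomarkers, up to five under the main schedule table.
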